11.6. Appendix 6: Derived and Transformed Data

11.6.1. General

Multiple Measurements at One Analysis Time Point

 • Mean of the measurements will be calculated and used in any derivation of summary statistics but if listed, all data will be presented. • If there are two values within a time window (as per Section 11.3.1) the value closest to the target day for that window will be used. If values are the same distance from the target, then the value for the earlier date will be taken. • Participants having both High and Low values for Normal Ranges at any post-baseline visit for safety parameters will be counted in both the High and Low categories of “Any visit post-baseline” row of related summary tables.
Study Day

 • Calculated as the number of days from First Dose Date: 
 • Ref Date = Missing → Study Day = Missing • Ref Date < First Dose Date → Study Day = Ref Date – First Dose Date • Ref Date ≥ First Dose Date → Study Day = Ref Date – (First Dose Date) + 1

11.6.2. Study Population

Duration of Follow-Up instead of Extent of Exposure																																

 • Number of days of follow-up after study drug administration will be calculated based on the formula by Overall and TCs: 																																

Duration of Follow-Up in Days = Date X – (Date Y) + 1
																																

For subjects who received GSK1358820 as first treatment
 
  
 Overall / TC for calculation	Subject status	X	Y	
   
 Overall	All subjects	Study Exit / Withdraw Date	1st treatment date	
 
 TC1	Study Exit or Withdraw in TC1	Study Exit / Withdraw Date [1]	1st treatment date	
 
 TC1	Receive next treatment	Date prior to 2nd treatment [1]	1st treatment date	
 
 GTC1	The same days as TC1	
 
 GTC2	Study Exit or Withdraw in TC2	Study Exit / Withdraw Date	2nd treatment date	
 
 GTC2	Receive next treatment	Date prior to 3rd treatment	2nd treatment date	
 
 GTC3	All subjects in GTC3	Study Exit / Withdraw Date	3rd treatment date	
  
	Overall / TC for calculation	Subject status	X	Y	Overall	All subjects	Study Exit / Withdraw Date	1st treatment date	TC1	Study Exit or Withdraw in TC1	Study Exit / Withdraw Date [1]	1st treatment date	TC1	Receive next treatment	Date prior to 2nd treatment [1]	1st treatment date	GTC1	The same days as TC1			GTC2	Study Exit or Withdraw in TC2	Study Exit / Withdraw Date	2nd treatment date	GTC2	Receive next treatment	Date prior to 3rd treatment	2nd treatment date	GTC3	All subjects in GTC3	Study Exit / Withdraw Date	3rd treatment date
Overall / TC for calculation	Subject status	X	Y																													
Overall	All subjects	Study Exit / Withdraw Date	1st treatment date																													
TC1	Study Exit or Withdraw in TC1	Study Exit / Withdraw Date [1]	1st treatment date																													
TC1	Receive next treatment	Date prior to 2nd treatment [1]	1st treatment date																													
GTC1	The same days as TC1																															
GTC2	Study Exit or Withdraw in TC2	Study Exit / Withdraw Date	2nd treatment date																													
GTC2	Receive next treatment	Date prior to 3rd treatment	2nd treatment date																													
GTC3	All subjects in GTC3	Study Exit / Withdraw Date	3rd treatment date																													

For subjects who received Placebo as first treatment
																																

Duration of Follow-Up instead of Extent of Exposure

Overall / TC for calculation	Subject status	X	Y
Overall	All subjects	Study Exit / Withdraw Date	2nd treatment date (1st treatment date of GSK1358820)
TC1	Study Exit or Withdraw in TC1	Study Exit / Withdraw Date [1]	1st treatment date
TC1	Receive next treatment	Date prior to 2nd treatment [1]	1st treatment date
GTC1	Study Exit or Withdraw in GTC1	Study Exit / Withdraw Date	2nd treatment date (1st treatment date of GSK1358820)
GTC1	Receive next treatment	Date prior to 3rd treatment	2nd treatment date (1st treatment date of GSK1358820)
GTC2	All subjects in GTC2	Study Exit / Withdraw Date	3rd treatment date (2nd treatment date of GSK1358820)
GTC3	Not applicable, because GSK1358820 treatment is allowed only two times for subjects who received Placebo as first treatment in this study.		

- [1] In interim analysis, use the following date:
 - Date of withdraw date for subjects who do not receive 2nd treatment and withdraw before week 24 after 1st treatment
 - Date of the Week 24 visit in treatment phase 1 for subjects who do not receive 2nd treatment and do not withdraw
 - Date prior to 2nd treatment for subjects who receive 2nd treatment at the Week 12 / 18 visit in treatment phase 1.

Duration of NDO history

- Duration of NDO history is defined as the duration (years) from the date of diagnosis to the date of screening visit.

Identification of anticholinergic drug and beta-3 agonist

- Since information of anticholinergic drug and beta-3 agonist was collected as 'prior NDO medication', it is needed to identify which codes will be regarded as anticholinergic drug and beta-3 agonist. Following code will be in SI dataset

Drug	Term Name	Code
Anticholinergics	FESOTERODINE	54026501
	FESOTERODINE FUMARATE	54026502
	IMIDAFENACIN	53735601
	OXYBUTYNIN	00538901
	OXYBUTYNIN HYDROCHLORIDE	00538902
	PROPIVERINE	01241601
	PROPIVERINE HYDROCHLORIDE	01241602
	SOLIFENACIN	53085701
	SOLIFENACIN SUCCINATE	53085702
	TOLTERODINE	01350201
	TOLTERODINE TARTRATE	01350202
	TOLTERODINE FUMARATE	01350203
beta-3 adrenergic receptor agonist	MIRABEGRON	54321501

[figure not shown]
11.6.3. Efficacy

Diary Data Convention
General Convention

 • For baseline and post-treatment visits, analyses will be based on the diary data collected during a 3-day interval for each visit. Each 3-day interval consists of 3 consecutive 24-hour periods, with the first period starting from the time of the first urinary episode on the first of the 3 days. • A valid diary day is defined as any of the three 24-hour periods with 2 or more any type of urinary episodes. Data collected from a 24-hour period with less than 2 urinary episodes (i.e., an invalid diary day) will be set to missing in this day. • For baseline and post-treatment visits, the 3-day diary will be determined based on the following algorithm: 
 • Apply assessment windows defined in Section 11.3.1, which are based on days from the date of study treatment. • Determine the time of the first urinary episode that is within the assessment window (in the example below, 7:30am on Apr3). Count forwards for 3 consecutive days (in the example below, APR3 is considered as 7:30am on Apr3 to 7:29am on APR4, APR4 is considered as 7:30am on Apr4 to 7:29am on APR5 and APR5 is

Diary Data Convention

considered as 7:30am on Apr5 to 7:29am on APR6 for diary data handling). As for volume voided, the time of the first collection of volume voided should be determined independently of the time of the first urinary episode. Note: the last 24-hour period should end within the window, i.e., prior or on the last day specified in the window definition; otherwise, the 24-hour data will not be used for the corresponding window. For baseline diary data, the urinary episodes that occurred on injection day but before the injection time will be counted for baseline diary data.

- Using the example below, the first 24-hour time period starts from 7:30am on Apr 3 and ends at 7:29am on Apr 4. The second 24-hour time period starts from 7:30am on Apr4 and ends at 7:29am on Apr 5. Note that this 24-hour is considered as an invalid diary day since it has only one episode during the 24 hours. The third or the last 24-hour time period starts from 7:30am on Apr 5 and ends at 7:29am on Apr6.
- At least one valid 24-hour diary day within the window is required for the visit. Otherwise, the 3-day diary data will be missing for the visit.

For diary data with a diary date but missing the urinary time, the diary time will be set to mid-day at 12:00pm.

Example for date of diary data handling

- Here, the example of handling of diary data of 3 consecutive days and its relation to assessment window is described for the case of TC1 week 12.
- As shown in 11.3.1, the target data of TC1 week 12 is day 85 and the assessment window of TC1 week 12 is from day 65 to day 106. The time of the first urinary episode should be within day 65 to day106 for diary data of TC1 week 12. In addition, only the data until day106 is available for TC1 week12.
- All examples below are assumed that valid diaries were taken for 3 consecutive days.
- In example 1, the first day is not from day 65 to day 106. Therefore, all the diary data for this visit are NOT available for TC1 week12.
- In example 2 and 3, all diary data are available because diary date for data handling are from day 65 to day 106.
- In example 4 and 5, a part of diary date for data handling is out the range (day 65-106). Diary of these days are regarded as invalid diary.

Example	The time of the first	After 3 consecutive	Diary date for	Available data for
---------	-----------------------	---------------------	----------------	--------------------

Diary Data Convention				
number	urinary episode	24-hour period (3 consecutive days)	data handling	diary data of TC1 week 12
1	Day 64 9:00am	Day 67 8:59am	Day 64, 65, 66	No data available
2	Day 65 9:00am	Day 68 8:59am	Day 65, 66, 67	All data available
3	Day 104 9:00am	Day 107 8:59am	Day 104, 105, 106	All data available
4	Day 105 9:00am	Day 108 8:59am	Day 105, 106, 107	Day 105 and 106 are available
5	Day 106 9:00am	Day 109 8:59am	Day 106, 107, 108	Only day 106 is available

Derivation of diary endpoints

- Following endpoint will be derived as “A” divided by “B”. “A” and “B” are defined below for each endpoint. Derivation should be done by visit. These derivations will be done by using only diary data in valid diary days.

For valid diary day, if no episodes are recorded, “A” on that day will be treated as zero.

Endpoint	A	B
Daily average number of urinary incontinence episodes	Number of “Yes” response to the diary question of “Did you have accidental urinary leakage?”	Number of valid diary days in the visit
Daily average number of voids	Number of “Yes” response to the diary question of “Did you urinate into the toilet?” Or “Yes” response to the diary question of “Did you use a catheter to urinate?”	
Average volume voided per void	The total volume collected in 24-hour period	Number of the urinary volume records which are not missing

- For the endpoint of Proportion of patients attaining 100%, ≥75% and ≥50% reduction from baseline in the daily average of urinary incontinence episodes, if change from baseline in the daily average of urinary incontinence episodes
 - is -100%, then this subject will attain 100%, ≥75% and ≥50%
 - falls the range (-100 <, <=-75%), then this subject will attain ≥75% and ≥50%
 - falls the range (--75 <, <=-50%), then this subject will attain ≥50%
is larger than -50%, then this subject will not attain any category

Handling of partial missing data in diary (except for urinary time)

- If the response to the diary question of “Record volume collected OR indicate “not collected” for

Diary Data Convention

each episode” is missing, then this response will be treated as missing, not zero of volume.
 
 As for other response, the missing response will be treated as missing. In other words, this is the same meaning to be treated as “No” to the response to the diary question.
Handling of missing urinary time

 For diary data with a diary date but missing the urinary time, the diary time will be set to mid-day at 12:00 pm at that day.
Handling of partial missing day in diary

 Partial missing day is defined as any missing diary day or invalid diary day in 3-day period. If there are 1 or 2 partial missing days in 3- day bladder diary, these days will be treated as missing and no imputation will be done for partial missing day. Therefore, endpoints in 3- day bladder diary will be calculated by using 1 or 2 valid diary data, if there is any partial missing day in the visit.
Definition of Incomplete 3-day diary

 Incomplete 3-day diary is defined as the diary which does not have 3 valid diary days.

KHQ Convention				
Derivation of KHQ domains				

Following table shows the derivation of KHQ domains [Committee for Preparation of the Clinical Guideline for Overactive Bladder, the Japanese Continence Society, 2015].
 
Only role limitations and social limitations will be analysed by ANCOVA model. Other domains will be only summarized.
				
Domain	ITEMS	Question in eCRF	scale	Derivation
General Health Perception	1 (1 item)		1= Very Good 2= Good 3= Fair 4= Poor 5= Very Poor	Domain Score = (score of left item -1) / 4 * 100
Incontinence Impact	2 (1item)		1= Not at all 2= A little 3= Moderately 4= A lot	Domain Score = (score of left item -1) / 3 * 100
Role Limitations	3a and 3b (2 items)		1= Not at all 2=Slightly 3=Moderately 4= A lot	Domain Score = (summed scores of left items -2) / 6 * 100
Physical Limitations	4a and 4b (2 items)		1= Not at all 2=Slightly 3=Moderately 4=A lot	Domain Score = (summed scores of left items -2) / 6 * 100
Social Limitations	4c, 4d, 5c (3 items)		0= N/A 1= Not at all	Domain Score = (summed scores of left

KHQ Convention				
Derivation of KHQ domains				
			2=Slightly 3=Moderately 4=A lot	items -3) / 9 * 100 If score of 5c = 0 then Domain Score = (summed scores of left items -2) / 6 * 100
Personal Relationships	5a and 5b (2 items)		0= N/A 1= Not at all 2=Slightly 3=Moderately 4=A lot	Domain Score = (summed scores of left items -2) / 6 * 100 If summed scores of left items = 1 then Domain Score = (summed scores of left items -1) / 3 * 100 If summed scores of left items = 0 then Domain Score will be treated as missing
Emotions	6a, 6b and 6c (3 items)		1= Not at all 2=Slightly 3=Moderately 4=Very Much	Domain Score = (summed scores of left items -3) / 9 * 100
Sleep/Energy	7a and 7b (2 items)		1= Never 2=Sometimes 3=Often 4=All the time	Domain Score = (summed scores of left items -2) / 6 * 100
Severity/Coping Measures	8a, 8b, 8c, 8d and 8e (5 items)		1= Never 2=Sometimes 3=Often 4=All the time	Domain Score = (summed scores of left items -5) / 15 * 100
Handling of partial missing data				

 If missing data exists in KHQ data in the visit, the corresponded item or domain will be treated as missing. 				

TBS
Answers and positive response of TBS

TBS (treatment benefit scale) consists of 4 answers to 1 questions “Please complete the following question by considering your current condition (urinary problems, urinary incontinence) compared to your condition before you received any study treatment in this trial”. Subjects will select their answer to this question considering their condition. Available answers are below and will be coded 1 to 4 in order to use statistical analysis.
 
 • 1 - Greatly improved • 2 - Improved • 3 - Not changed • 4 - Worsened 
The answers of 1 – Greatly improved or 2 – Improved will be regarded as positive response.
 
Other answers including missing data will be regarded as NO positive response.

Urodynamics
Urodynamics Data Convention for No IDC occurred

To take into account that there will be subjects post-treatment in whom an involuntary detrusor contraction was confirmed as not occurring during urodynamics, the data will be analysed below.
 
 • Maximum detrusor pressure during the first IDC ($P_{\max IDC}$) A value will not be imputed for subjects with no IDC since MDP during first IDC cannot be evaluated. • Volume at first IDC ($V_{P_{\max IDC}}$) A value will be imputed by MCC for subjects with no IDC.

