- (d) Diary must have been completed for any 3 consecutive days in the week prior to the visit (for screening phase only, it could have been completed for 3 consecutive days at any time during the screening phase). The volume voided is recorded by subjects for one 24-hour period during the 3 day diary collection period.
- (e) Only serious adverse events assessed as related to study participation or a GSK product will be recorded from the time when a subject consents
- (f) Measured only body weight
- (g) Urine culture and sensitivity is performed by the central laboratory when dipstick results are positive for nitrites or leukocyte esterase.
- (h) For patients with doubtful reaction in urinary pregnancy test, the investigator (or subinvestigator) may conduct serum pregnancy test.
- (i) For patients without a UTI as determined from the urinalysis or urine culture and/or investigator opinion, prophylactic antibiotic are to be administered 1 to 3 days before study treatment, on the day of treatment, and 1 to 3 days after treatment. For patients with a UTI as determined from the urinalysis or urine culture and/or investigator opinion, an antibiotic to which the identified organism is sensitive is to be administered at least 5 days prior to study treatment and continued for at least 3 days following the procedure.
- (j) If qualification for re-treatment criteria was met, the patient will undergo the exams specified in Table 2, column marked "If qualification for re-treatment criteria was met".
- (k) Patients who are not re-treated will remain in Treatment phase 1 and continue to visit at the scheduled study visit.
- (l) Patients who are using the medications or therapies urinary incontinence due to NDO should maintain the same dose from at least 7 days before the start of the screening phase throughout Treatment phase 1.
- (m) Samples may be collected during the screening period through Day 1 (prior to randomization)

**Table 2 Time and Events Table [Treatment phase 1 (if qualification for re-treatment criteria was met) to treatment phase 2]**

	Treatment phase 1	Treatment phase 2															
Week	If qualification for re-treatment criteria was met (Within 21 days prior to re-treatment)	1st re-treatment	Re-treatment (1st)							2nd re-treatment	Re-treatment (2nd)					Withdrawal	

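### SAP 11.6.3 discards a whole diary that starts a day before its window, so a compliant diary on Days 29–31 gives no Week 6 primary value (1 of 75 visit/start combinations)

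*SAP*

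**What the plan says.** **Diary timing.** Protocol Table 1, footnote (d): "Diary must have been completed for any 3 consecutive days in the week prior to the visit". Protocol 7.3.1.1 excludes the visit day itself. Table 1 allows the Week 6 visit a tolerance of 7 days either way.

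**Analysis windows.** SAP 11.3.1 counts the treatment date as Day 1. Week 2 runs from Day 2 to Day 29, and Week 6 from Day 30 to Day 64 with target Day 43. These rows apply to efficacy data generally; no parameter is named.

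**Start of the window.** SAP 11.6.3 illustrates the rule with Week 12, where "the assessment window of TC1 week 12 is from day 65 to day 106". It requires the first urinary episode to fall inside those days. Example 1 starts on Day 64: "In example 1, the first day is not from day 65 to day 106". None of that diary is used, although Days 65 and 66 lie inside the window.

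**End of the window.** Example 4 starts on Day 105 and overruns, yet "Day 105 and 106 are available". Example 5 starts on Day 106 and keeps that day. Of the diaries that fit, the SAP says "In example 2 and 3, all diary data are available because diary date for data handling are from day 65 to day 106".

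**The Note.** Under General Convention, the SAP says "the last 24-hour period should end within the window, i.e., prior or on the last day specified in the window definition". A period that fails this condition is left out of that window's data.

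**What follows if a value is missing.** One valid diary day is enough for a visit value (SAP 11.6.3). The MMRM imputes nothing (SAP 11.7.3). In the binary analyses, missing data up to Week 12 count as non-response under the DO=NR rule (SAP 7.2.5.1).

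**The concern.** The windows are centred on visit days, but the diary is kept in the week before the visit, so a diary sits systematically early in its window. A rule that rejects a diary for starting one day too soon therefore acts on the side where compliant diaries lie. Only Week 6 has an opening day late enough for this to matter, and Week 6 is the primary time point.

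A subject who attends on an allowed day and completes the diary on allowed days could have no observed primary endpoint value. The same subject would be scored as not attaining the 50%, 75% or 100% reduction at Week 6, despite having recorded data. No reason is given for treating the two ends of the window differently.

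**Working it through.** **Step 1. Reproduce the SAP's five examples (window Day 65–106, first episode at 9:00).**

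Two rules were applied, both requiring the diary to start inside the window:

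- Start-day rule: keep the period starting on day *d* if *d* ≤ 106.
- Note read by clock end: that period ends at 8:59 on day *d*+1, so keep it only if *d*+1 ≤ 106.

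| Example | Start | SAP keeps | Start-day rule | Note by clock end |
|---|---|---|---|---|
| 1 | 64 | none | none | none |
| 2 | 65 | 65, 66, 67 | 65, 66, 67 | 65, 66, 67 |
| 3 | 104 | 104, 105, 106 | 104, 105, 106 | 104, 105 |
| 4 | 105 | 105, 106 | 105, 106 | 105 |
| 5 | 106 | 106 | 106 | none |

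The start-day rule reproduces 5 of 5. The clock-end reading differs in Examples 3, 4 and 5.

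**Step 2. Earliest compliant diary start at each scheduled cycle 1 visit.**

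Earliest start = target day − visit tolerance − 7.

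| Visit | Earliest start | Window opens |
|---|---|---|
| Week 2 | 15 − 3 − 7 = 5 | 2 |
| Week 6 | 43 − 7 − 7 = **29** | **30** |
| Week 12 | 85 − 7 − 7 = 71 | 65 |
| Week 18 | 127 − 7 − 7 = 113 | 107 |
| Week 24 | 169 − 7 − 7 = 155 | 149 |
| Week 30 | 211 − 7 − 7 = 197 | 191 |
| Week 36 | 253 − 7 − 7 = 239 | 233 |
| Week 42 | 295 − 7 − 7 = 281 | 275 |
| Week 48 | 337 − 7 − 7 = 323 | 317 |

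Only Week 6 fails, by one day.

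**Step 3. Count the Week 6 combinations.** Visit days 36 to 50 give 15 values. With three consecutive days inside the seven before the visit, the start can be visit − 7 to visit − 3, which is 5 values. 15 × 5 = 75. A start before Day 30 needs visit − 7 < 30, so the visit must be on Day 36 and the start on Day 29: 1 of 75, or 1.3% if all combinations were equally likely.

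**Step 4. What happens to that diary (Days 29, 30, 31).** Under the start rule and Example 1, Week 6 receives nothing. By analogy with Example 5, its Day 29 could count toward Week 2. A compliant Week 2 diary lies within Days 5–17, at most 10 days from target Day 15, against 14 for Day 29, so the closest-to-target rule (SAP 11.6.1) would prefer it.

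**Step 5. Reach of the Note.** At Week 6 the clock-end reading changes only diaries starting on Days 62–64. The latest compliant start is 50 − 3 = Day 47. Enumeration over all scheduled cycle 1 visits finds no compliant diary where the Note and the examples differ.

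**Step 6. Scale of one lost value.** Protocol 9.2.1 gives 26% power. A two-sided 5% two-sample *t* test with noncentrality 1.5 / (3.0 × √(1/n₁ + 1/n₂)) gives 26.2% at 15 and 15, and 25.5% at 14 and 15. This is only a gauge, since the trial tests no formal hypothesis.

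**The case against.** The strongest reply is that this is a corner case. It needs the earliest allowed visit day together with the earliest allowed diary days. The subject stays in the MMRM through the other visits under the stated missing-at-random assumption, and the effect on information is below one percentage point of power. All of that stands, and it limits the point to a minor one.

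A second reply is that the General Convention locates the first episode inside the window and counts forward, which could be read as keeping Days 30 and 31. That reading is available, but the worked-example section then requires the diary's first episode to be in the window, and Example 1 drops a diary with two in-window days. The explicit example is what a programmer would follow.

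Two stronger readings are tempting and are not supported:

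- A reader might infer that the Note contradicts Examples 3–5 and that this is what loses the primary value. The SAP does use the word ends for clock time ("The third or the last 24-hour time period starts from 7:30am on Apr 5 and ends at 7:29am on Apr6"), so the Note is loosely worded. However, the same section also labels each 24-hour period by its start date, and on that reading the Note agrees with all five examples. The table of examples tells a programmer what to do. The Day 29 loss comes from the start-of-window rule, and deleting the Note would leave it in place.
- A reader might infer that diaries from re-treatment qualification visits near later boundaries (Days 106/107, 148/149, 190/191) are widely affected. Such diaries can straddle a boundary, but compliant scheduled diaries for Weeks 12, 18 and 24 lie on Days 71–91, 113–133 and 155–175, and the closest-to-target rule would select them. The boundary diary matters mainly when the scheduled one is missing.

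**Conclusion.** The point holds as a minor one. The plan's start-of-window rule can discard a protocol-compliant Week 6 diary that has two days inside the window, whereas diaries overrunning the other end keep their in-window days. The subject then has no observed primary endpoint value and is counted as a Week 6 non-responder for incontinence reduction.

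The exposure is 1 of 75 compliant combinations at Week 6 and none at any other scheduled cycle 1 visit. With 30 subjects the expected loss is well under one: 30 × 1/75 = 0.4 if every subject attended compliantly and all combinations were equally likely, which is an assumption. If it happened, 1 of 15 observed Week 6 values in an arm would go.

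The conclusion assumes that Example 1 governs, that the visit falls on Day 36 with the diary begun on Day 29, and that no other diary falls in Days 30–64. The wording of the Note is a separate drafting matter with no effect on compliant scheduled diaries in cycle 1.

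**What to change.** Treat both edges alike: keep the diary days that fall inside the window whichever edge the diary crosses, and revise Example 1 accordingly (Days 65 and 66 kept). For the Week 6 case this retains Days 30 and 31, which meets the one-day minimum if at least one is a valid diary day.

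Alternatively, open Week 6 at Day 29 and close Week 2 at Day 28. That loses 0 of 75 compliant Week 6 combinations and 0 of 35 at Week 2 (7 visit days × 5 starts). The SAP 11.3.1 rows cover all efficacy data, so the change would reach beyond the diary, but compliant Week 2 visits fall on Days 12–18 and are not affected. Cycles 2 and 3 use the same limits, so their rows should be changed to match.

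Separately, reword the Note so that each 24-hour period is assigned by its start day, as all five examples do. The cost is a few lines of SAP text and the matching derivation code, settled before unblinding. No data collection or protocol change is needed.

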#### **7.3.1.3.1. King's Health Questionnaire (KHQ)**

Impact of urinary incontinence on QOL will be assessed using KHQ in accordance with the study schedule.

KHQ was developed by Kelleher et al. as questionnaire to assess impact of urinary incontinence on QOL. [Kelleher, 1997] The KHQ was translated into Japanese by Honma et al., and its appropriateness was verified in Japanese patients with urinary incontinence. [Honma, 1999; Honma, 2002]

KHQ is a questionnaire with 21 items and consisted by 9 domains: (i) General health, (ii) Incontinence impact, (iii) Role Limitations, (iv) Physical limitations, (v) Social limitations, (vi) Personal relationships, (vii) Emotion, (viii) Sleep/energy, (ix) Severity measure. The scores are summated according to an algorithm provided by Kelleher et al. [Kelleher, 1997]

Investigators/subinvestigators or the persons assisting with the trial will provide a KHQ questionnaire and instruct subjects to select the one most appropriate answer for each question.

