### 12.3.4. Recording of AEs and SAEs

AEs and SAE Recording:

 
• When an AE/SAE occurs, it is the responsibility of the investigator to review all documentation (e.g., hospital progress notes, laboratory, and diagnostics reports) relative to the event.
 
• The investigator will then record all relevant information regarding an AE/SAE in the CRF
 
• It is not acceptable for the investigator to send photocopies of the subject's medical records to GSK in lieu of completion of the GSK, AE/SAE CRF page.
 
• There may be instances when copies of medical records for certain cases are requested by GSK. In this instance, all subject identifiers, with the exception of the subject number, will be blinded on the copies of the medical records prior to submission of to GSK.
 
• The investigator will attempt to establish a diagnosis of the event based on signs, symptoms, and/or other clinical information. In such cases, the diagnosis will be documented as the AE/SAE and not the individual signs/symptoms.
 
• Subject-completed Value Evidence and Outcomes questionnaires and the collection of AE data are independent components of the study.
 
• Responses to each question in the Value Evidence and Outcomes questionnaire will be treated in accordance with standard scoring and statistical procedures detailed by the scale's developer.
 
• The use of a single question from a multidimensional health survey to designate a cause-effect relationship to an AE is inappropriate.
 

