11.7.2. Handling of Missing Data

Element	Reporting Detail
General	
 • Missing data occurs when any requested data is not provided, leading to blank fields on the collection instrument: 
 ○ These data will be indicated by the use of a “blank” in subject listing displays. Unless all data for a specific visit are missing in which case the data is excluded from the table. ○ Answers such as “Not applicable” and “Not evaluable” are not considered to be missing data and should be displayed as such.
Outliers	
 • Any participants excluded from the summaries and/or statistical analyses will be documented along with the reason for exclusion in the clinical study report.

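### Is the KHQ Personal Relationships score wrong when one of its two items is answered not applicable?

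*SAP*

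**What the plan says.** The KHQ derivation table in SAP 11.6.3 gives Personal Relationships two items, 5a and 5b, each coded 0 (not applicable) or 1 to 4. The default score is the sum less 2, divided by 6, times 100. There are two exceptions. A sum of 0 makes the domain missing. For a sum of 1: "If summed scores of left items = 1 then Domain Score = (summed scores of left items -1) / 3 * 100".

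Two other rows of the table bear on this. Incontinence Impact, a single item coded 1 to 4, is scored "Domain Score = (score of left item -1) / 3 * 100". Social Limitations has three items and tests the optional one directly: "If score of 5c = 0 then Domain Score = (summed scores of left items -2) / 6 * 100".

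The KHQ missing-data line reads "If missing data exists in KHQ data in the visit, the corresponded item or domain will be treated as missing". SAP 11.7.2 says that answers such as not applicable "are not considered to be missing data and should be displayed as such", so that line does not pick up a single not-applicable answer.

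On where the scoring comes from, SAP 11.6.3 introduces the table with "Following table shows the derivation of KHQ domains" and credits a Japanese clinical guideline on overactive bladder. Protocol 7.3.1.3.1 says "The scores are summated according to an algorithm provided by" the questionnaire's developers. Protocol 12.3.4 says questionnaire responses "will be treated in accordance with standard scoring and statistical procedures detailed by" the developer of the scale.

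**The concern.** A formula that spans 0 to 100 is written out, but it can be reached only at its lowest point. When one item is not applicable and the other is answered 2, 3 or 4, the 0 code goes into the two-item sum as if it were an answer below the lowest real one. The domain then cannot exceed 33.3. An answer of 2 beside a not-applicable item scores 0, the same as an answer of 1 on both items. The sum cannot separate these cases: a sum of 2 is either (0,2) or (1,1). Social Limitations, the row just above, tests the item itself and still reaches 100.

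If the trigger were a copying error, an affected subject's score would be too low and the change from baseline distorted. Change in KHQ domain score is a listed secondary endpoint, and two of the tables that carry it (2.47 and 2.48) are produced at the interim analysis for regulatory submission.

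**Working it through.** The plan gives no figure to reproduce, so the check applies the rule to every possible answer pair. All inputs come from the derivation table in SAP 11.6.3. Write S for 5a + 5b.

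**1. What the exception does.** S = 1 arises only from (0,1) and (1,0). The branch gives (1 − 1)/3 × 100 = 0. Without it, the default would give (1 − 2)/6 × 100 = −16.7.

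**2. One item not applicable, the other answered k.**

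| k | SAP as written | Single-item formula, (k − 1)/3 × 100 | Gap |
|---|---|---|---|
| 1 | 0 (exception) | 0 | 0 |
| 2 | (2 − 2)/6 × 100 = 0 | 33.3 | 33.3 |
| 3 | (3 − 2)/6 × 100 = 16.7 | 66.7 | 50.0 |
| 4 | (4 − 2)/6 × 100 = 33.3 | 100 | 66.7 |

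There are 5 × 5 = 25 pairs: 1 with both items not applicable, 8 with exactly one, and 16 with both answered. The two rules differ only for k = 2, 3 or 4 with either item not applicable, which is 3 × 2 = 6 pairs.

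**3. Where the exceptions sit.** The default gives (0 − 2)/6 × 100 = −33.3 at S = 0, −16.7 at S = 1, 0 at S = 2 and 100 at S = 8. The two sums with their own branch are exactly the two at which the default is negative. A rule meant only to keep scores from going below 0 would look like this.

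**4. Would rescaling be free of distortion?**

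*Same item not applicable at both visits.* The SAP rule shrinks change. From 4 to 3 it shows 16.7 − 33.3 = −16.7, against 66.7 − 100 = −33.3 rescaled. From 2 to 1 it shows 0, against −33.3.

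*An item becomes not applicable between visits.* Let a be the answer that drops out and b the answer that stays the same. For b of 2 or more, the SAP change is [(b − 2) − (a + b − 2)]/6 × 100 = −a/6 × 100. The rescaled change is [2(b − 1) − (a + b − 2)]/6 × 100 = (b − a)/6 × 100. For b = 1 the two rules agree.

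- (4,4) to (0,4): SAP −66.7, rescaled 0.
- (1,4) to (0,4): SAP 33.3 − 50 = −16.7, rescaled 100 − 50 = +50.
- (1,3) to (0,3): SAP 16.7 − 33.3 = −16.7, rescaled 66.7 − 33.3 = +33.3.

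Comparing the size of b − a with a over the 12 combinations with b of 2 or more, rescaling moves the score less in 8, equally far in 2 ((1,2) and (2,4)), and further in 2 ((1,3) and (1,4)). It does better more often, but it is not neutral.

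**5. What the score feeds.** SAP 11.6.3 and Table 2.49 restrict the KHQ ANCOVA to Role Limitations and Social Limitations. Personal Relationships appears only in the summary tables 2.47, 2.48 and 2.50 to 2.53, and KHQ data are listed by subject in Listing 34. SAP 2.4 states that the study has no formal hypotheses.

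**The case for a change.** The case for changing the rule is that the oddity shows from the text alone. The formula is reachable only at 0, a not-applicable code is counted as an answer below the scale, and the neighbouring row handles the same situation by testing the item. No other rule rescues it. The remedy is cheap: one check, a blinded count of one-not-applicable answers, and one line of derivation. The SAP has already used a blind review for the percent-change endpoints, and the two documents credit scoring to different sources, which is a reason to look.

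The arithmetic in that case stands in full. The inference to an error does not. For a published questionnaire the defect would be departure from the published rule, and neither source is available here to show one. The comparison with Social Limitations cuts both ways, since whoever wrote the table used an item test in one row and a sum test in the next. Incontinence Impact was designed as a single item, so its formula need not govern a two-item domain. The 33.3 ceiling is the same trigger described again, not separate evidence. SAP 11.7.2 concerns blank fields and display; the real support is the 0 code in the table itself. Replacing the rule without knowing its origin could also cost comparability with trials scored by the sum rule.

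**Conclusion.** The rule behaves as described: 6 of the 25 answer pairs score 33.3, 50.0 or 66.7 points lower than the SAP's single-item formula would give. Whether that is a slip in transcription or the published scoring cannot be settled from the protocol and SAP, and the position of the two exceptions fits a deliberate floor at 0 equally well.

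No amendment follows. The plan already names its scoring sources, and checking a programmed questionnaire derivation against the cited source is normal validation; a copying error would come to light there. If the rule is as published, it should stay as the reported score. A rescaled version would be a matter of preference, with distortions of its own when an item becomes not applicable.

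The consequence is small under either reading. Only the descriptive summaries of one of nine KHQ domains could move; the primary endpoint and every planned ANCOVA are untouched. The documents do not say how many subjects would mark exactly one of the two items as not applicable, and it may be none. The effect on an arm's mean change has no fixed sign: it depends on whether the subject improves or worsens and on whether the same item is not applicable at both visits.
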